1. BACKGROUND AND RATIONALE

1.1 Background

Chronic obstructive pulmonary disease (COPD) is currently the most common chronic respiratory disease in China, with a high prevalence of 13.7% (Wang C et al. 2018) and it is also the third leading cause of death (Stanaway J D et al. 2019), which causes a huge economic and social burden. Patients with exacerbation history or high symptom burden will have higher future risk of exacerbations, accelerated lung function decline, greater risk of cardiovascular events and higher mortality rates (Jones, R. C. M. et al. 2014, Kostikas, K. et al. 2020, Larsson, K. et al. 2019, Donaldson, G. C. et al. 2010, Kunisaki, K. M. et al. 2018).

But because the symptom of COPD is not typical and the public disease awareness is low, the diagnosis and treatment of COPD are seriously inadequate in China, there is only 5.9% of patients had ever been tested by spirometry in the history and 11.7% were taking treatments for COPD (Fang L et al. 2018). Therefore, the current management of COPD patients is poor, with low standard of care, a lack of regular pharmacological and non-pharmacological intervention, insufficient follow-up and disease education in the Chinese COPD clinical practice even in those high risk patients.

A pilot study of COPD management status in Guangdong province shows that only 28% of COPD patients received long-acting inhaled maintenance medication, 2.9% of smoking patients received smoking cessation intervention, and only 7.4% of patients received documented disease education in real world(Qiu Chen et al. 2019). The pilot study showed that in China, the standardized management of COPD is poor, we have a huge opportunity to improve the status.

1.2 Rationale

Due to the lack of quality control standards for the standardized management of COPD in China, Quality Standards (QS) has been published in 2022. The Quality Standards aims to

standardize COPD management in clinical practice in China, including diagnosis, assessment, pharmacological and non-pharmacological intervention, and follow-up. According to the COPD guideline and previous study (Ferrone M et al. 2019, Chen X R C et al. 2021), patients can benefit from standardized clinical behaviours, to be identified early, to be accessed comprehensively, to be treated correctly according to guidelines, and with appropriate follow-up to improve adherence.

The QIP study focuses on improving disease management of COPD patients who have a history of exacerbation, and with a scope to optimize their current COPD management according to medical history record. Acute exacerbation is a crucial issue that cannot be ignored in the management of COPD. COPD diagnosed patients with frequent exacerbation have been found to have more severe airflow limitation, heavier symptom burden, increased mortality rate, and worse quality of life (QoL) (Soler-Cataluna J J et al. 2005, Kerkhof M, et al. 2019, Le Rouzic O et al. 2018, Donaldson G C et al. 2002). These patients are at a higher risk of future events(such as exacerbations, hospital admission, or death) but there is an opportunity to modify that risk and improve outcomes through thorough standardized patient management.

The QIP study aims to evaluate the impact of QS implementation on target patients in intervention group (receive QS implementation) compared to control group(maintain current practice) in a real-world setting, including but not limited to exacerbation, lung function, quality of life, and treatment pattern.

2. OBJECTIVES

QIP study aims to evaluate the impact of QS implementation through patient outcome. The objective needs to be addressed in a real-world setting to demonstrate the true benefit of QS implementation on target population compared with control group.

2.1 Primary objective

Primary Objective	Outcome Measure
To evaluate the effectiveness of QS implementation on clinically important deterioration (CID)	Time to CID, which is defined as the time from the date of enrolment until the date of the first CID. CID is defined as any of the following events: 1) Trough FEV ₁ decline $\geq 100\text{ml}$ 2) CAT increasing ≥ 2 unit 3) one moderate or severe exacerbation

2.2 Secondary objectives

Secondary Objective:	Outcome Measure:
To evaluate the impact of QS implementation on exacerbations, lung function and symptoms in COPD patients	
• Annual rate of moderate or severe exacerbation• Annual rate of severe exacerbation• Change from baseline in trough FEV₁ over 48 weeks• Change from baseline in CAT over 48 weeks

To describe COPD management and treatment adherence in QS implementation group and usual care group	
• Proportion of patients received inhalation technique review at least once during follow-up period• Proportion of patients received long-acting inhaled medicine with percentage of days covered (PDC) $\geq 80\%$ over 48 weeks
To describe treatment pattern in stable COPD for intervention group and control group	
• Proportion of prescription of inhaled maintenance medicine at 12, 24, 36, 48 weeks• Proportion of patients prescribed ICS-containing inhaled maintenance medicine at 12, 24, 36, 48 weeks.

[figure not shown]
3. METHODOLOGY

3.1 Study Design

This is a interventional, cluster-randomized, pragmatic clinical study. Totally, there are 41 sites will be selected across China, It is worth mentioning that leading site will directly enter the intervention group, mainly be in charge of supervising and managing the QS implementation in the sites of intervention group. The rest 40 sites will be randomized (stratified by tier levels and geographic region) to the intervention group or control group at the ratio of 1:1. In the intervention group, QS implementation will be performed, and will be checked every 12 weeks. The control group will maintain the current practice. Eligible patients will be recruited and followed up every 12 weeks for 48 weeks.

Eligible consented patients will be enrolled consecutively to minimize selection bias (see section 3.3.2 and section 3.3.3 for inclusion and exclusion criteria).

Figure 1. study schematic

Leading site will directly enter the intervention group, and will recruit at least 27 patients, supervises and manages the QS implementation in the sites of intervention group.

3.2 Intervention

The QIP study is based on implementation of the Quality Standards into routine care, supported by data collection and analysis as core components. Figure 2 is a visual representation of QS, with the centre of the figure describing the components needed to implement the Quality Standards into practice. All components in bold text in Figure 2 are core components for the study and should be implemented by independent sites.

[figure not shown]
3.2.1 Quality Standards

The “Chinese Quality Standards of COPD Clinical Care” (known as the Quality Standards or QS) have been agreed by a panel of 17 experts in COPD, also involved by national COPD guideline. The Quality Standards aim to provide a framework of quality improvement efforts in COPD patients. There are three evidence-based Quality Standards encompassing clinical assessment, pharmacological and non-pharmacological intervention, and patient follow-up which are outlined in Figure 2.

Figure 2 also shows where the target populations link with the Quality Standards and provides a broad outline of how the study flows.

The study targets patients who have a confirmed COPD diagnosis and with high-risk of future events. Patients are scheduled for clinical disease assessment using the components described in QS 1 (section 3.2.2.2.a). Pharmacological and non-pharmacological interventions are then initiated based on the information obtained during disease assessment (QS 2, section 3.2.2.2.b). Depending on the intervention required, follow-up and patient review is carried out using QS for those whose COPD is not stable or controlled (QS 3, section 3.2.2.2.c). The follow-up recommendations then ensure patients are regularly reviewed and reassessed to improve the quality of patient care and management.

Figure 2. Key components of Quality Standards for target population and process

3.2.2 QS implementation

Quality Standard has core components and requirements that must be implemented in order to translate it into practice, and these are described in section 3.2.2.2.

3.2.2.1 Translating the Quality Standards into practice

The intended pathway and interlinking of the Quality Standards during implementation of the QS is shown in Figure 2. Different hospitals may differ, however, to translate the Quality Standards into practice the following requirements must be adhered to. Where acceptable, options to modify these components to suit each hospital needs are provided.

a) QS 1:Assessment of disease and quantification of future risk

Eligible patients following the QS 1 assessment process goes on to have a thorough clinical assessment to characterise their disease status. This clinical assessment will also consider the patient's risk of future exacerbations, cardiac events and mortality.

Assessment of disease

- **Symptom assessment** to be performed during follow-up period.
 - The COPD Assessment Test (CAT) (Jones et al. 2009, Jones et al. 2012) score (Appendix 2)(developed to quantify symptom burden in COPD using a concise and simple set of questions) is the core symptom assessment method in the QS. It is referred to frequently in COPD guidelines and is used to help guide treatment.
 - Symptom assessment should be performed at least every 12weeks, but may be performed more frequently depending on frequency of patient review and disease stability.

- **Exacerbation Risk** Number and severity of exacerbations since previous review to be recorded in EMR.

Quantification of future risk

- **Comorbidities** including osteoporosis, diabetes mellitus, gastroesophageal reflux disease (GERD), anxiety and depression to be actively sought and managed.
- **Risk prediction** QS will be used to quantify risk of future events and/or mortality. Details regarding specific risk score methods used should be documented and available for sharing with the QC team where possible.
 - Information resulting from risk assessment to be conveyed to patient when felt to be beneficial by healthcare provider.

b) **QS 2: Pharmacological and non-pharmacological interventions**

Following thorough assessment, QS 2 focuses on ensuring patients receive therapy and intervention in line with their risk and clinical parameters. The focus in QS 2 is to identify opportunities to increase or alter treatment such that health outcomes are improved. The following list of pharmacological and non-pharmacological interventions are core components of the QS and should be routinely applied.

- **Initial therapy for newly diagnosed** patients to be based on China COPD guideline classification and recommendations
- **Modification of therapy** for high-risk patients to be made in accordance with current China COPD guideline follow-up pharmacological treatment algorithms, utilizing information obtained during assessment. The focus is on inhaled maintenance therapy, other COPD therapies to be evaluated in accordance with China COPD guideline.
- **Smoking cessation intervention(s)** such as referral to smoking cessation services and prescription of pharmacotherapy for smoking cessation to be offered at initial assessment and subsequent review as required.

- **Pulmonary rehabilitation** according to need and physician's recommendation.
- **Vaccination** pneumococcal and influenza vaccines will be recommended.

c) **QS 3: Appropriate follow-up**

COPD is a chronic disease and effort to optimise management must continue beyond initial assessment or diagnosis in the provision of regular multi-faceted follow-up consultations.

- **Medication and symptom review** must involve the recording of current therapy, medication adherence, exacerbation history since previous review and current symptoms.
- **Inhaler technique** to be reviewed at least once during study period and corrections in technique made as necessary.
- **Spirometry** performed for monitoring purposes and to detect those with rapid decline in FEV1 (defined as more than 40ml per year (Vestbo J et al. 2011)).

3.2.2.2 Quality Control (QC) team

Implementation of QS requires input from some clinical staffs of participating hospitals.

The QC team members are recommended to be directors of respiratory departments from participating hospitals and should familiarise themselves with the Quality Standards and core QS components(Figure 2).

The QC team responsibilities include:

- Coordination of overall delivery of the QS
- Facilitate understanding of the overall project objectives and rationale
- Ensure the site-level delivery of QS education and training
- Assess the site-level QS implementation and quality
- Collect feedback of physicians from respiratory departments from participating hospitals

- Regular check implementation performance and review implementation process. This may be achieved by a sub-group in the team who are responsible for ongoing assessment of the programme, and for making recommendations for modifications where necessary.

The QS training will be performed every 3 months by the QC team, the initial one will be a comprehensive face-to-face training and with a full test before sites launch. And the training content of next 3 times during study period will be determined based on the assessment and feedback of implementation sites.

The control group will maintain their usual care. COPD usual care is decided by the physician based on the clinical practice.

Patients in both groups will be trained of exacerbation identification.

3.2.2.3 Quality Control indicators

The Quality Control Indicators (QCI) are linked to the Quality Standards described in Figure 2 , reflecting the physicians' standardized behaviours to manage the COPD populations. The Quality Control Indicators(QCI) should be checked by QC team every 3 months.

[figure not shown]
The checking items including % of patients receiving inhalation therapy, non-pharmaceutical treatment , exacerbations treatment, % of patients who had been given the COPD disease education during visit, etc. the details showed in Appendix 1.

QC team could make modifications of training content according to the QCI assessment and feedback where necessary.

3.2.3 Monitor progress and sustain improvement

QS has to be practiced in the intervention group, thus a crucial part of the programme for implementing sites is the cyclical review of the implementation process and outcomes achieved throughout the program. This iterative process(Figure 3) is used to identify on-going opportunities for program enhancement and make the necessary modifications to existing approaches that will continuously improve patient outcomes.

Figure 3. QS education and improvement process

3.2.4 Data source(s)

The Electronic Data Capture (EDC) system will be used for data collection and query handling. Participating patients will be followed up for at least 48 weeks for data collection. This will include data from the EMR, medical charts, and other sources in healthcare centres in the intervention group and control group. CAT score will be collected through questionnaire. Patient questionnaire will be collected in CRF by a study staff who will not be involved in recruitment and training.

3.3 Study Population

3.3.1 Hospital selection criteria

Totally 41 hospitals across China will be included, and 40 hospitals will be allocated via cluster-randomization to the intervention or control groups (20 hospitals*2). Leading site will directly enter the intervention group, mainly be in charge of supervising and managing the QS implementation in the sites of intervention group. So a total of 41 hospitals should meet the following criteria will be considered for inclusion in this study:

- Tier 2 or tier 3 hospitals.
- Equip with standardized spirometers and technicians meeting ATS criteria.
- No implementation of QS or similar programs before study entry.
- Have established department of Pulmonary and Critical Care Medicine, emergency unit, and the corresponding wards.

- Availability of COPD maintenance inhaled medicines (at least one mono , one dual, and one triple inhaled therapy should be available) recommended by the China COPD guideline.

3.3.2 Inclusion criteria

Patients are eligible to be included in the study if all of the following criteria apply:

- Diagnosed with COPD
- Aged 40 years or older
- CAT ≥ 10
- With exacerbation history:
 - at least 2 moderate or 1 severe exacerbation in the previous year;
 - or 1 moderate exacerbation in the previous year with FEV1 <50% predicted value at baseline;
- Must able to sign the informed consent form

3.3.3 Exclusion criteria

Patients will be excluded from this study if any of the following exclusion criteria apply:

- Patients on triple therapy at baseline with a LAMA, LABA, and inhaled corticosteroid (ICS) combination (Including open triple and fix-dose triple)
- Significant diseases or conditions other than COPD, which, in the opinion of the Investigator, may put the subject at risk because of participation in the study or may influence either the results of the study or the subject's ability to participate in the study
- Patients who are currently involved in any other interventional studies

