3.3.4 Subject enrolment

Potentially eligible patients will be screened, investigators should keep a record of subjects who screened for this study. Patients who meet the inclusion criteria will be enrolled. Investigators should keep a record of subjects who entered this study.

The Investigators will:

- Obtain signed informed consent from the potential subject or their guardian/legal representative before any study specific procedures are performed.
- Assign potential subject a unique enrolment number.
- Determine subject eligibility. See Section 3.2.2 and Section 3.2.3

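### Investigators who probably know their hospital's arm may exclude patients whose other conditions might influence the study results, so selection could differ between arms in either direction

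*Protocol*

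**What the plan says.** - **The criterion.** Protocol 3.3.3 excludes significant diseases or conditions other than COPD on any of three grounds: risk to the patient, possible influence on the results, or effect on the ability to take part. The second ground reads "may influence either the results of the study". All three are judged "in the opinion of the Investigator". No list of conditions or threshold is given.
- **Who decides.** Under 3.3.4 the investigators "Determine subject eligibility" and keep a record of the patients screened. That section does not ask for the reason a patient was excluded.
- **When the arm is known.** Under 3.1, 40 hospitals are "randomized (stratified by tier levels and geographic region) to the intervention group or control group at the ratio of 1:1". Section 3.2.2.2 provides training every three months, of which "the initial one will be a comprehensive face-to-face training and with a full test before sites launch".
- **Comorbidities.** Under QS 1 (3.2.2.1), osteoporosis, diabetes and reflux disease are listed along with "anxiety and depression to be actively sought and managed". QS 1 opens with "Eligible patients following the QS 1 assessment process goes on to have a thorough clinical assessment". Table 1 in 6.1 has comorbidities recorded from visit 0, with no distinction by arm.
- **Stated safeguard.** Section 3.1 says "Eligible consented patients will be enrolled consecutively to minimize selection bias".

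**The concern.** Randomising hospitals gives comparable patients only if the rule for letting patients in works the same way in both arms. Here the rule includes a forecast of outcome, made by someone who can be taken to know the allocation. An investigator who expects a patient with, say, unstable heart disease to deteriorate can exclude that patient on this ground alone, with no need to show risk to the patient or inability to attend.

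If the limb is used more freely in one arm, case mix differs by arm before the intervention has acted. The primary analysis in 5.3.2 is a clustered log-rank test for which no covariates are named. Covariates are named only for the secondary models in 5.3.3, and comorbidity is not among those listed. A shift in case mix would therefore pass into the primary comparison.

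The bias section (5.4.1) deals with the choice of hospitals, data collection and contamination. It does not deal with the selection of patients after hospitals have been allocated.

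**Working it through.** **1. Is the arm known at screening?** No sentence says so. It follows from hospital-level allocation (3.1) and from training and testing intervention hospitals before launch (3.2.2.2). The protocol describes no concealment from recruiters and no independent check of eligibility.

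**2. Does a stated safeguard limit the discretion?**
- Consecutive enrolment (3.1) applies to eligible, consented patients, so it acts after the criterion has been used.
- The nurse in 5.4.1 collects data and is kept out of recruitment.
- The screening record (3.3.4) would show how many were screened, but reasons are not required.

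**3. Can the QS 1 comorbidity search reach enrolment?** Not directly, since it is written for patients already eligible. An indirect route exists. Under 3.3.5 a patient later found not to meet the criteria must be withdrawn, and under 5.1 a patient with no post-baseline efficacy assessment is outside the full analysis set. A condition found early after enrolment could remove a patient that way. This is possible, not shown.

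**4. How large could the effect be?** The protocol gives no figure for this point, so none can be reproduced. The following is an illustration.

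Inputs from the protocol (5.2 and Table 1): hazard ratio 0.70, 80% power, two-sided 5%, control median 121 days, follow-up 336 days.

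Assumptions that are not in the protocol: 20% of candidates have twice the CID hazard, a share e of them is excluded in the intervention arm and none in the control arm, and there is no true effect.

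- Standard error of the log hazard ratio implied by the stated power: |ln 0.70| / (1.960 + 0.842) = 0.3567 / 2.802 = 0.127.
- Base hazard h per day: solve 0.8x + 0.2x² = 0.5 with x = exp(−121h). Then x = 0.5495 and h = 0.5987 / 121 = 0.00495.
- Share of high-hazard patients left in the intervention arm: 0.2(1 − e) / (1 − 0.2e). This is 0.111 for e = 0.5 and 0.158 for e = 0.25, against 0.200 in the control arm.
- Ratio of mean hazards at time zero: 1.111 / 1.200 = 0.926 for e = 0.5, and 1.158 / 1.200 = 0.965 for e = 0.25.
- High-hazard patients have their events first, so this ratio moves towards 1. Solving the Cox score equation over 336 days with equal arms gives a hazard ratio of 0.947 (log −0.0541) for e = 0.5 and 0.975 (log −0.0257) for e = 0.25.
- Two-sided rejection probability, Φ(d − 1.96) + Φ(−d − 1.96), with d = |log HR| / 0.127:

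| Share excluded, one arm only | d | Apparent HR | False positives |
|---|---|---|---|
| one half | 0.425 | 0.947 | 0.062 + 0.009 = 7.1% |
| one quarter | 0.202 | 0.975 | 0.039 + 0.015 = 5.5% |

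If the control hospitals do the excluding, the hazard ratios invert to about 1.06 and 1.03, with the same rejection probabilities.

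**5. Range.** Let 10% to 30% of candidates be sicker, with 1.5 to 2 times the hazard, and let 50% to 100% of them be excluded in the intervention arm only. Here the standard error comes from 713 events and a design effect of 1 + 20 × 0.079 = 2.58, that is √(4 × 2.58 / 713) = 0.120. The apparent hazard ratio then runs from 0.98 to 0.83 and the false-positive rate from about 5% to about 34%. The upper end needs every sicker patient to be excluded in one arm and none in the other.

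**The case against.** The strongest defence is that nothing shows the arms would behave differently. The criterion is the same in both arms and applies only to significant conditions. Osteoporosis or reflux, which QS 1 names, would not obviously qualify. Medical history, comorbidities and a full physical examination are recorded at visit 0 for all patients, which narrows any gap in detection. All of this stands.

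A reader might infer that the limb will be used more in intervention hospitals, because their physicians are told to look for comorbidities. The documents do not support this: QS 1 follows the eligibility decision, and the withdrawal route in 3.3.5 is only a possibility. A reader might also take the time-zero ratio of 0.93, which would give about 9% false positives, as the size of the bias. That overstates it, because the ratio shrinks during follow-up.

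Two further objections have some force. The wider weakness is recruitment by staff who know the allocation, since whom they approach and who consents are open to the same influence. The two retained limbs also rest on the investigator's opinion. These limit what the fix can achieve. They do not justify keeping a ground for exclusion that turns on expected influence on the results.

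**Conclusion.** The point holds as a weakness of design, not as a demonstrated bias. The text allows an outcome-based exclusion by investigators who can be inferred to know their arm, and no stated safeguard limits it. Whether the arms would differ, and in which direction, is not established.

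Under the central assumptions in the working, the apparent hazard ratio with no true effect is about 0.95 to 0.975 and the false-positive rate about 5.5% to 7%. The second case is barely distinguishable from the nominal 5%. Larger effects need strong, one-sided exclusion. The change is worth making because it is cheap and the limb is hard to defend in an openly allocated trial that calls itself pragmatic. The trial's validity does not hang on it.

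**What to change.** 1. In 3.3.3, delete the limb on influence on the study results. Keep the limbs on risk to the patient and ability to participate.
2. In 3.3.4, require the reason for each exclusion to be entered in the screening record that is already kept.
3. Report the numbers screened, excluded (by reason) and enrolled, by arm. If the SAP already provides this, a cross-reference is enough.

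The cost is a short amendment, one more field in the screening record and a table. The population becomes slightly more mixed, which suits a pragmatic trial. Because the retained limbs still depend on investigator opinion, a determined recruiter could use them instead. The route is narrowed and made visible, not closed.
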